#### b. The practical implementation, intervention and scope

Six nursing homes in Odsherred City, Region Zealand, Denmark, participate in the project, and estimated 100 older adults is expected to be enrolled in the project. There will be ongoing inclusion.

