#### Sample size calculation:

Initially the power calculation is performed by the individual randomization, calculated on the basis of the 30 secound chair stand test. The starting point is six nursing homes is involved in the study. Approximately 40-50 residents are living in each location and assumable half of them are Ow/O and wants to participate in the project. (n=20). A desired detectable change of 1.3 (39), a P-value <0.05 and a power of 80%. The study has two arms (control and intervention) and the standardized difference in the nursing center incl. intra cluster correlation, SD diff, nursing center = 0.42.  $SD(\text{diff.}, \text{nursing center}) = (SD(\text{diff.}, \text{person}))/\sqrt{n}$ , SD diff, person  $\approx 1.87$  If SD is 1.87 or less, the power will be at least 80% or greater. If there are more than 20 people per. care center power will increase and if there are fewer than 20 people power will decrease. After sub study 1 a more accurate number can be provide, also knowing what is feasible in sub study 2.

Approximately 100 participants will be included and cluster randomized to either 6 month of nutritional and physical intervention or 6 month of usual care (control). A simple random sample without replacement will be selected by a non-project group member using the lottery method. Effects from the intervention will be examined by mixed methods that include both quantitative and qualitative data, as well as action research that focuses on creating development and change in collaboration with participants and care staff at the nursing homes.

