#### Intervention

The intervention is developed with a focus on nutritional needs and physical activities.

In follow-up, the PDSA model (25,26) is used to redefine issues and relevant actions together with care staff, the nursing home management and participants. The intervention will be developed on

the basis of new knowledge from sub-study 1, previous studies, practical experiences, the participant's experiences and wishes as well as the staff's experiences and wishes. Together they will be form an implementation catalog, from here, the nursing homes can select a relevant number of components, which will be tested and implemented in practice. An example could be that the general offer of diet type at the nursing home is changed to the diet type "normal" diet for older adult with a high protein content instead of enriched diet type for malnourished older adults (4). Whether the participants are at nutritional risk is assessed by Ernæringsvurderingsskemaet (EVS), and the participants who need a enriched diet or special diet forms such dysphagia diet (4), is of course offered / continues these diets . However, it may be that some participants can achieve / maintain a better physical function with a normal diet.

The implementation duration is 6 months and the PDSA model (25,26) repeated at two-month intervals to strengthen and qualify the intervention. The PDSA model is known to the city's staff in advance, and is additionally used in connection to continuing education. In addition, every day physical activities that contributes to maintaining / improving physical functional is included, based on the potentials that are uncovered in sub-study 1.

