#### All outcome measures

Data are collected at baseline and 6 months (m). The starting point is the same measurements as described in sub-study 1, combined with feasibility in practice.

The data analysis takes into account that not all participants are included in all measurements.

Tabel 1: Data collection in sub study 2

Variable	Method	Baseline	6 m
Age and sex	Journal data	x	
Weight	Calibrated standard weight as part of routinely weighing, Journal data	x	x
Weight, fat%, fat mass (kg), muscle mass (kg), bone mass (kg), BMI, total body water (TBW), TBW%, intracellular water and extracellular water	BIA	x	x
Calf circumference	Measured by non-elastic plastic tape		
Height	Journal data	x	
Height measured	Measured standing or lying	x	
Chronic disease, diagnosis and number	Journal data	x	
Muscle function	30 s CST , gait speed and HGS	x	x
Nutritional risk	EVS	x	x
Quality of Life	ASCOT questionnaire	x	x

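### Inclusion is ongoing while six whole homes are allocated by an undated lottery, and nothing places consent and baseline before the draw or closes enrolment

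*Protocol*

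**What the plan says.** Section 3b of the protocol, on practical implementation, says "There will be ongoing inclusion". It gives no closing date or closing event.

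The unit of allocation is the home. Section 3a (Sample size calculation) describes the draw as follows: "A simple random sample without replacement will be selected by a non-project group member using the lottery method". Section 3c gives three control and three intervention homes. The draw has no date and no stated position relative to consent or baseline. The only wording that hints at an order is in section 3a: "Approximately 100 participants will be included and cluster randomized to either 6 month of nutritional and physical intervention".

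Section 12 has the principal investigator, care staff and relatives speak with residents, who then have 24 hours to decide. Section 9 has the principal investigator and trained students collect the data. Under Intervention in section 3b, "the nursing homes can select a relevant number of components" from a catalogue and put them into practice. One possible component given there is that "the general offer of diet type at the nursing home is changed". The same section says "The implementation duration is 6 months".

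Section 4 plans an intention-to-treat analysis, defined by data arising after randomisation, and an ANCOVA adjusted for baseline and potential confounders.

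**The concern.** With six clusters, a single draw fixes the arm of everyone who enters afterwards. Randomising homes protects the comparison only for residents who were enrolled without knowledge of the arm. If staff approach residents differently once the arm is known, or residents accept differently, the two groups can differ for reasons unrelated to the intervention. Intention-to-treat does not help, because the selection happens at entry. Baseline-adjusted ANCOVA removes only what is measured and modelled.

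There is a secondary, conditional point. If a home chooses a component that applies to the whole home, a late entrant's baseline might be taken when exposure has already begun. Should an effect have appeared by then, part of it would be hidden.

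The study is called a feasibility trial, and its specific objectives concern components, feasibility and screening. It nevertheless powers a between-arm comparison (section 3a), names functional primary outcomes (section 3b) and plans a paper on effects (section 13). The comparison therefore needs protecting.

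**Working it through.** **1. Order of events, as far as the protocol fixes it**

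| Event | Where | Position relative to the draw |
|---|---|---|
| Information, 24 hours, consent | Section 12 | Not stated |
| Baseline measurement | Section 3b, All outcome measures | Not stated |
| Lottery | Section 3a | No date |
| Inclusion | Section 3b | Ongoing, no end |

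No entry excludes a resident consenting and being measured after the draw.

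**2. Who would know the arm**

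Care staff of an intervention home must know it once components are chosen and in use, and care staff take part in recruitment. The principal investigator both recruits and collects data. No section says that recruiters or assessors are kept unaware of the arm.

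**3. The plan's own power figure**

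Inputs from section 3a: difference 1.3 stands, P < 0.05, home-level SD 0.42, person-level SD about 1.87, 20 residents per home. From section 3c: 3 homes against 3. Two-sided testing is assumed, as the protocol does not state it.

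- SE = SD_home × √(2/3) = 0.42 × 0.8165 = 0.343
- Noncentrality = 1.3 / 0.343 = 3.79, t-test on home means, 4 df, critical value 2.776
- Power = 80.6%, so the stated 80% is reproduced

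**4. What late entry could do (illustration, assumed inputs)**

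Let a fraction f of intervention-home residents enter after the draw, with selection shifting their chair-stand change by b stands. The bias is f × b. With SD_home 0.42, the two-sided false-positive rate moves from 5% as follows:

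| f | b | Bias | Share of 1.3 | False-positive rate |
|---|---|---|---|---|
| 0.10 | 0.5 | 0.05 | 4% | 5.2% |
| 0.25 | 1.0 | 0.25 | 19% | 8.8% |
| 0.50 | 1.0 | 0.50 | 38% | 20.4% |
| 0.50 | 1.87 | 0.94 | 72% | 54.3% |

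Neither f nor b is in the protocol. The table shows only that the consequence can be negligible or serious.

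**5. Power if fewer residents are enrolled before the draw**

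The protocol's formula is SD_home = 1.87 / √n, with n = N/6:

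- N = 100: n = 16.7, SD_home 0.458, power 73.9%
- N = 80: n = 13.3, SD_home 0.512, power 64.9%
- N = 60: n = 10, SD_home 0.591, power 53.3%

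The formula has no separate between-home term, although section 3a describes 0.42 as "the standardized difference in the nursing center incl. intra cluster correlation". As a check, let SD_home² = s² × (ICC + (1 − ICC)/n), with s² set so that SD_home is 0.42 at n = 20. The ICC values are assumed:

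- ICC 0.02: power 75.5%, 68.7% and 59.1% at N = 100, 80 and 60
- ICC 0.05: power 77.1%, 72.2% and 64.8%

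The counts of 80 and 60 are assumptions too.

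**The case against.** The best counter-reading is that ongoing inclusion means rolling enrolment across the six homes up to the draw, and that the wording in section 3a, which puts inclusion ahead of cluster randomisation, gives the intended order. There is supporting context. Sub-study 1 measurements are the starting point, residents' wishes feed into the intervention before homes choose components, and written information covers both sub-studies. Many residents may therefore be engaged early. This lowers the risk but does not remove it. None of it says that sub-study 2 consent or baseline precedes the lottery, and none of it bars later entry. The unseen SAP does not fill the gap either, because the order of consent, baseline and randomisation is trial conduct, which an analysis plan cannot restore afterwards.

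A reader might infer three stronger things that the protocol does not support:

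- **That residents will be recruited after allocation, so the comparison is biased.** The text permits such recruitment but does not prescribe it.
- **That late baselines will be taken under exposure.** The home-wide diet change is offered only as an example, and the components have not been chosen.
- **That late entrants must get less than 6 months of intervention.** This assumes one implementation calendar per home. Section 3a can equally be read as 6 months per participant, so the point is only that the protocol does not say which.

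**Conclusion.** The point stands as a gap in the recruitment and randomisation sequence that should be closed. The protocol contains a positive rule of open-ended inclusion, an undated allocation of whole homes, and nothing that orders one before the other. Followed as written, it allows recruitment and baseline measurement by people who know the arm.

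This is a risk of selection bias, not a demonstrated bias. Its size depends on how many residents enter late and how strongly they are selected, and the protocol gives neither. The exposed-baseline point is conditional on the components chosen. Confidence is medium, because inclusion before the draw may well be the intention.

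**What to change.** Replace the ongoing-inclusion sentence in section 3b with: *Residents in all six homes are consented and measured at baseline before the lottery is drawn, and this cohort forms the primary between-arm comparison; residents who join later may take part, are reported by arm as entering after allocation, and enter only a secondary or sensitivity analysis.*

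Two matching edits are needed:

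- **Section 4.** Define the intention-to-treat population as all residents enrolled before the draw, analysed by their home's allocation. Without this, the present reference to data after randomisation conflicts with a pre-draw primary cohort.
- **Sections 3a and 3b.** State whether the 6 months runs per home or per participant, so that a late entrant's follow-up is defined.

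The cost is these text changes and the order of the start-up steps. The real downside is that recruitment must be largely complete before the draw, and precision falls if it is not. Relative to 100 residents, the protocol's formula loses about 9 points of power at an assumed 80 and about 21 at an assumed 60. With an assumed ICC of 0.02 to 0.05 the losses are about 5 to 7 and 12 to 16 points. The figure of about 74% at 100 is already implied by the existing plan, whose 80% rests on 20 residents per home (120 in all), so it is not a cost of this change. Late entrants can still take part, which keeps the pragmatic and feasibility aims intact.

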#### Intervention

The intervention is developed with a focus on nutritional needs and physical activities.

In follow-up, the PDSA model (25,26) is used to redefine issues and relevant actions together with care staff, the nursing home management and participants. The intervention will be developed on

the basis of new knowledge from sub-study 1, previous studies, practical experiences, the participant's experiences and wishes as well as the staff's experiences and wishes. Together they will be form an implementation catalog, from here, the nursing homes can select a relevant number of components, which will be tested and implemented in practice. An example could be that the general offer of diet type at the nursing home is changed to the diet type "normal" diet for older adult with a high protein content instead of enriched diet type for malnourished older adults (4). Whether the participants are at nutritional risk is assessed by Ernæringsvurderingsskemaet (EVS), and the participants who need a enriched diet or special diet forms such dysphagia diet (4), is of course offered / continues these diets . However, it may be that some participants can achieve / maintain a better physical function with a normal diet.

The implementation duration is 6 months and the PDSA model (25,26) repeated at two-month intervals to strengthen and qualify the intervention. The PDSA model is known to the city's staff in advance, and is additionally used in connection to continuing education. In addition, every day physical activities that contributes to maintaining / improving physical functional is included, based on the potentials that are uncovered in sub-study 1.

#### Primary outcome

Primary outcome is sustained or improved muscle function (30 - second chair stand test (30 s CST), gait speed (10 meters) and hand grip strength (HGS))

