## **STUDY Protocol Sub-study 2: Interventions focusing on nutrition and physical activities for overweight and obese older adults in nursing homes "IFEBO" (A feasibility study)**

**Authors:** [name], [name], [name], [name] and [name]

- 1. Title for the project:** Interventions focusing on nutrition and physical activities for overweight and obese older adults in nursing homes "IFEBO"
- 2. Purpose:** The overall purpose is to investigate how muscle function and care-related quality of life can be maintained or improved through nutrition and physical activity interventions in older adults in nursing homes. Older adults with the combination of both overweight and T2D have a special focus in the sub-study, as the two conditions together increased the demands on the nutritional intervention.
  - a. Specific objectives:**
    - What components of existing practice should be included in interventions focusing on nutrition and physical activities?
    - What interventions are feasible in practice?
    - Does the screening model identify the older adults in need of a nutrition and physical activity intervention?

The project's hypothesis is that the older adults with Ow/O may be malnourished and may benefit from interventions that combine nutrition and physical activities.

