#### **c. Deviations from standard care**

Control group include three nursing homes and participant will follow standard care. The interventions group including three nursing homes will implement the intervention developed on

the basis of new knowledge from sub-study 1, previous studies, practical experiences, the participant's experiences and wishes as well as the staff's experiences and wishes.

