#### **4. Statistical analysis**

The analysis follow the intention-to-treat principle and thereby including all data after randomization, regardless of non-compliance or lack of results.

The effect of measures and intervention is assessed using covariance analysis (ANCOVA) adjusted for baseline and potential confounders. Kaplan-Meier analysis and parametric or non-parametric regression and correlation analyzes are used to assess data in a timeline perspective with multiple measurements of physical functioning, weight, muscle mass, and care-related quality of life.

Data on recruitment and participants' feasibility and compliance in relation to intervention will be assessed by descriptive and comparative analyzes.

A statistical software program for scientific research e.g. SPSS or R will be used for statistical analyzes.

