## **12. Recruitment of subjects and informed consent**

Recruitment of project participants takes place from Odsherred city's 6 nursing homes. The first step in recruitment takes place by principal investigator orally and in writing informing the nursing homes, care staff, relatives, nursing home councils and the residents of the nursing homes about the project's purpose, content and course. Posters are posted telling about the project. In the next step, (oral information) the principal investigator, the care staff and relatives talk to the residents.

Participant information (written information) is provided for both sub-studies as well as the leaflets "Subjects' rights in a health science research project", and "Before you decide - to be in health science experiments". The written information contains a description of the project, its purpose, method and possible consequences associated with the participants' participation. Participation in the project is voluntary, and the participants have the opportunity, without further justification, to interrupt the collaboration and their participation in the project. In the third step, the residents then have 24 hours to decide whether they want to participate in the project and sign a declaration of consent. During the project period, the participants can obtain further information about the project from the principal investigator. Collection, storage and processing of empirical data is done with the Danish Data Protection Agency's instructions for handling confidential information in research work of an empirical nature.

Participants have the opportunity to withdraw consent at any time during the project. If there are measurements, eg performance tests, which the participants do not want to participate in, available data is collected from the journaling system (CURA) without participation in all measurements.

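### Three unranked tests share the primary outcome, but the stated P<0.05 and 80% power cover only the 30-second chair stand

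*Protocol*

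**What the plan says.** The Primary outcome section (under 3b) reads: "Primary outcome is sustained or improved muscle function (30 - second chair stand test (30 s CST), gait speed (10 meters", and then adds hand grip strength. The three tests stand side by side, with no lead measure, composite or success rule. Table 1 also puts them in one row, measured at baseline and 6 months.

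The Sample size calculation (under 3a) is "calculated on the basis of the 30 secound chair stand test". Its targets are: "A desired detectable change of 1.3 (39), a P-value <0.05 and a power of 80" per cent. It uses a home-level SD of 0.42, obtained from a person-level SD of about 1.87 with 20 residents per home. No target difference or SD for gait speed or grip strength appears anywhere.

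On allocation, section 3c says: "Control group include three nursing homes and participant will follow standard care". The other three homes receive the intervention. On analysis, section 4 says: "The effect of measures and intervention is assessed using covariance analysis (ANCOVA) adjusted for baseline and potential confounders". It does not rank the three tests.

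**The concern.** A primary outcome should tell the reader which result decides the trial, and the sample size should refer to that result. Here the outcome section gives three tests equal standing and the sample size section serves one of them. The error rate and power then depend on a success rule that the protocol does not state. If any one test suffices, the false-positive rate exceeds 5%. If all three are needed, power falls below 80%. Because the protocol itself fixes both the outcome definition and the power basis, this is not a multiplicity method left for a statistical analysis plan.

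A lesser point is the word 'sustained'. No margin is given for it, while the ANCOVA in section 4 tests a difference between arms. If the word stays, a non-significant difference could be presented as success, although the protocol does not say that it will be.

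Table 2 in section 13 plans a paper on the effects of the intervention on physical function, so the choice of deciding test will matter to readers.

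**Working it through.** **Inputs from the protocol.** Difference 1.3 stands; home-level SD 0.42; P<0.05; stated power 80% (Sample size calculation). Three homes per arm (section 3c).

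**Step 1: reproduce the stated power.** Compare home means with a two-sample t-test:
- SE = 0.42 × √(2/3) = 0.343
- df = 3 + 3 − 2 = 4; t(0.975) = 2.776
- Non-centrality = 1.3 / 0.343 = 3.79
- Two-sided power from the noncentral t = **80.6%**

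The SD that gives exactly 80% is 0.423. The protocol does not state sidedness. Reading 0.42 as the standard error of the arm difference, one-sided with 4 df, gives 81.2%. On either reading the stated 80% belongs to one test of the chair stand.

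**Step 2: error rate if any one of three tests counts.** With independent tests, 1 − 0.95³ = 0.143. Correlated cases were simulated with 3 v 3 home means and a pooled t with 4 df (2,000,000 trials). The correlations are assumptions, since the protocol gives none.

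| Correlation | Any test, two-sided (nominal 5%) | Any test, favourable direction (nominal 2.5%) |
|---|---|---|
| 0 | 14.3% | 7.3% |
| 0.5 | 13.3% | 6.6% |
| 0.7 | 12.0% | 6.0% |
| 0.9 | 9.4% | 4.7% |

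A normal approximation gives slightly lower two-sided values (12.5% at 0.5, 10.9% at 0.7), with the same conclusion.

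**Step 3: power if all three must be significant.** Assume that gait speed and grip strength have the chair stand's standardised effect (1.3/0.42 on home means). Independent tests give 0.806³ = 0.523. Simulation (1,000,000 trials) gives 52.3%, 59.6%, 64.4% and 71.3% at correlations 0, 0.5, 0.7 and 0.9, against the stated 80%.

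**Step 4: three primaries with a Bonferroni split.** At 0.05/3 = 0.0167 per test, chair-stand power for 1.3 falls from 80.6% to 53.0%. Power for at least one success (600,000 trials, same equal-effect assumption) is 89.6%, 82.0%, 76.3% and 66.8% at the four correlations.

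**Step 5: what a non-significant result would show.** The 95% CI half-width for the chair stand is 2.776 × 0.343 = 0.95 stands, and 0.95/1.3 = 73% of the target difference. A non-significant result therefore cannot by itself show that function was sustained.

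**The case against.** The protocol's calculation is correct and openly based on the chair stand, and it claims 80% power for nothing else. The chair stand is listed first and is the only powered measure, so muscle function might be read as the construct and the chair stand as its sizing measure. That reading is possible, but the protocol does not state it. If it was the intention, the fix only puts it into words.

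The figures in Steps 2 to 4 presuppose success rules, correlations and equal effects that the protocol does not supply. This stands: they are scenarios, and none is the trial's actual error rate or power. They show how far the answer moves with the reading.

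The point about 'sustained' is weak on its own. The Purpose section asks how "muscle function and care-related quality of life can be maintained or improved through nutrition and physical activity interventions", so the word may only express the hoped-for direction. It is best treated as a wording note.

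The study is labelled a feasibility study, and the protocol says that a more accurate sample size may follow sub-study 1. Both lower the stakes. The stated 80% power and the planned paper on effects keep the point from being trivial.

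Finally, the 80% needs 20 residents per home. The protocol expects about 100 in six homes, or 16.7 each. By its own formula the home-level SD is then 1.87/√16.7 = 0.458 and chair-stand power is 73.9%. That is a separate shortfall, which naming one primary outcome neither causes nor cures.

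**Conclusion.** The concern holds. The outcome section makes three tests equally primary, while the sample size section supports only one, and no other section resolves this. On the protocol's own inputs the stated 5% and 80% are right for a single chair-stand test. For the trio, the error rate could be roughly 9% to 14% under an any-of-three rule, or joint power roughly 52% to 71% under an all-three rule. Those ranges rest on assumed correlations from 0 to 0.9, and the power range also on equal standardised effects. The mismatch itself needs no assumption, because it can be read directly from the two sections. It should be corrected, but given the feasibility label it is not a fatal fault.

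**What to change.** Name one primary outcome that matches the sample size: the baseline-adjusted difference in the 30-second chair stand between intervention and control at 6 months. Make gait speed and hand grip strength secondary. Remove 'sustained' from the primary definition, report the share of residents without decline by arm descriptively, and do not present a non-significant difference as sustained function. Report by arm how many residents complete the chair stand at baseline and at 6 months.

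The cost is rewording the outcome section, since all three tests are already collected at both visits. There are two downsides. Gait speed and grip strength can no longer carry the primary claim. The primary result also comes to depend on residents who complete the chair stand, and the protocol expects gaps. Under All outcome measures it says: "The data analysis takes into account that not all participants are included in all measurements". Section 12 makes provision for refusals: "If there are measurements, eg performance tests, which the participants do not want to participate in". Hence the request for completion counts.

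A workable alternative is to keep three primaries under a stated any-of-three rule with a Bonferroni split. Its power (Step 4) depends on effects for gait speed and grip strength that the protocol does not support with figures, so a target difference and SD for each would have to be added.
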